5.1.1 Data Collection

The data will be collected specifically for this project. The information obtained in this study will be recorded in such a manner that the identity of the human subjects cannot be ascertained directly. The data will not contain personally identifiable information and will be labeled using a coding system. The data labels will contain the subject code, date and time of recording, and mode and condition of recording. Only the principal investigator, [name], will have access to the centrally and electronically stored and password-protected subject identification list to decode data files. All other study investigators will have access to the de-identified data. All study investigators will use encrypted research computers.

Data Recording

Case report forms for each subject will be used to enter clinical evaluation results, and scores of paper-pencil tests, surveys, and performance-based tests. All of this information will

then be entered into a password-protected electronic database, which will be stored in a group-owned ([name] Lab) shared space on a Yale REDCap database. This is a secure web application for building and managing online surveys and databases. It is specifically geared to support online or offline data capture for research studies and operations.

Imaging data obtained at the MRRC will be transferred securely to workstations for analysis and stored on HIPAA-compliant secure central storage servers ("Storage@Yale") provided by the Yale IT Department for a monthly fee. All team members will use encrypted research computers.

Sources of Data

Initial Screening: Data will be collected at meetings with the subjects via phone call and Zoom video platform.

- Demographic data (age, sex, ethnicity, level of education, etc.)
- MRRC MRI safety questionnaire
- Medical history questionnaire
- MoCA test for global cognition
- PD Cognitive Functional Rating Scale for daily functional abilities

Online Surveys: These surveys will be administered via the Yale REDCap online survey platform to those who pass the initial screening. The selected surveys aim to evaluate the contribution of nonmotor factors (e.g., mood disorders, fatigue) to cognitive functioning. The survey data will be exported from REDCap.

- Geriatric Depression Scale
- Parkinson Anxiety Scale
- Starkstein Apathy scale
- PD Quality of Life Questionnaire-39
- Parkinson Fatigue Scale
- Scales for Outcomes in Parkinson's Disease – Sleep

Online Homework and Quizzes: These will administered via the Yale REDCap online survey platform. Responses will be exported from REDCap.

- Quizzes on the psychoeducation material for the PD-Con group
- Surveys on the content of mental imagery homework for the PD-MI group

Clinical and Cognitive Evaluations:

- MDS-UPDRS and Hoehn & Yahr to assess disease severity (Visit 1)
- Wechsler Test of Adult Reading to determine premorbid IQ (Visit 1)
- RBANS test and executive function tests (Stroop, letter fluency (F-A-S), and Trail Making Test parts A and B) for a comprehensive cognitive evaluation (Visits 1, 3, and 4)
- Neuro-QoL survey (primary cognitive outcome) to assess the impact of cognitive functioning on activities of daily living (Visits 1, 3, and 4)
- Structured cognitive interview for the PD-MI group to determine subjects' cognitive difficulties during everyday tasks (Visit 1)
- QMI Vividness of Imagery Scale will serve as a manipulation check for the mental imagery intervention (Visits 2, 3, and 4)

- Modified Six-Elements Test as a performance-based measure of goal-directed planning and execution (Visits 1, 3, and 4)

Case report forms for each subject will be used to enter clinical evaluation results, and scores of paper-pencil tests, online surveys, and performance-based tests. All of this information will then be entered into a password-protected electronic database, which will be stored in a group-owned ([name] Lab) shared space on a Yale REDCap database.

Imaging Data:

Functional MRI data during mental imagery and video-watching tasks will be collected in a 3 Tesla human magnet at the MRRC (Visits 2, 3, and 4). The fMRI data will be used for functional connectivity analyses to evaluate the changes in whole-brain functional connectivity (primary imaging outcome) and other network measures as a result of the mental imagery intervention.

Imaging data will be transferred securely to workstations for analysis and stored on HIPAA-compliant secure central storage servers ("Storage@Yale") provided by the Yale IT Department for a monthly fee.

5.1.2 Adverse Events Definition and Reporting

An Adverse Event will be defined as any untoward or unfavorable occurrence in a human research subject (physical or psychological harm) temporally associated with the individual's participation in the research (whether or not considered related to participation in the research).

Attribution of Adverse Events:

Adverse events will be monitored for each subject participating in the study and attributed to the study procedures / design by the principal investigator, [name], according to the following categories:

Definite: Adverse event is clearly related to investigational procedures

Probable: Adverse event is likely related to investigational procedures

Possible: Adverse event may be related to investigational procedures

Unlikely: Adverse event is likely not to be related to the investigational procedures

Unrelated: Adverse event is clearly not related to investigational procedures

Plan for Grading Adverse Events:

The severity of adverse events noted during the study will be graded as mild, moderate, or serious.

Plan for Determining Seriousness of Adverse Events

In addition to grading the adverse event, the principal investigator will determine whether the adverse event meets the criteria for a Serious Adverse Event (SAE). An adverse event is considered serious if it results in any of the following outcomes:

- 1- Death
- 2-A life-threatening experience in-patient hospitalization or prolongation of existing hospitalization;
- 3-A persistent or significant disability or incapacity;
- 4-A congenital anomaly or birth defect; OR
- 5-Any other adverse event that, based upon appropriate medical judgment, may jeopardize the subject's health and may require medical or surgical intervention to prevent one of the other outcomes listed in this definition.

An adverse event may be graded as severe but still not meet the criteria for a SAE. Similarly, an adverse event may be graded as moderate but still meet the criteria for an SAE. The principal investigator will consider the grade of the event as well as its "seriousness" when determining whether reporting to the IRB is necessary.

Reporting of Adverse Events

Adverse events will be reported in accordance with federal and Yale University IRB rules. For each adverse event, the principal investigator, [name], will record the onset, end, intensity, required treatment, outcome, seriousness, and action taken. Serious or unexpected adverse events will be reported to the Yale University IRB, within 5 days. Expected or non-serious adverse events will be reported at the time of continuing review.

We will submit information summarizing the number and frequency of adverse events experienced by participants in each group, regardless of whether or not they were anticipated or unanticipated. We will also provide the time frame for adverse event data collection and specify whether the collection approach for adverse events was systematic or non-systematic.

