As a covered entity, Yale School of Medicine provides HIPAA Zoom accounts. The HIPAA-compliant and password-protected Zoom conferences will be conducted using an encrypted computer connected to the Yale secure network. The HIPAA Zoom has different features than the regular Zoom: 1) The ability to export, copy/paste or save chats is disabled. 2) Screen capturing and sending images are also disabled. 3) All messages are encrypted. 4) Cloud recording is disabled. Recordings are saved locally. To ensure security, each time a different invitation link with a unique meeting ID and password will be emailed to the subjects individually. As soon as the subject joins, the meeting will be locked to prevent others from joining. Meetings will be recorded by the research team to facilitate the collection of mental imagery content. Once the data has been transcribed, the videos will be deleted. Subjects will be permitted to record the meetings as well. Zoom software will be updated regularly to ensure that new security features are incorporated.

Due to the Covid-19 pandemic, the Yale Human Research Protection Program prepared an online Remote Research Visit Source Document for remote research visits conducted using Zoom or telephone in accordance with the ICH Good Clinical Practice standards of ALCOA-C [Attributable, Legible, Contemporaneous, Original, Accurate and Complete]. The document includes detailed information that needs to be entered (protocol number, PI, subject code, visit type/number/date, name of staff conducting the remote visit, documentation of the consent process, type of protocol assessment (e.g., demographics, medical history, questionnaires, etc.), details of intervention, and side effects). After each telephone encounter and Zoom visit this online document will be filled out and maintained with subjects' research records.

Upon completion of the study, study binders will be stored in a locked facility for the amount of time required by law. After this time, the study binders will be destroyed by shredding. The electronic database that contains the information in case report forms will stay on the password-protected research computer until the study closes. The link to personal information will be kept until the end of the study, after which time the link will be destroyed and the data will become anonymous. The data will be kept in this anonymous form indefinitely.

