Mental Imagery Training: Subjects in the PD-MI group will receive personalized training during one-on-one sessions 3 times a week for the first 4 weeks. Training will be offered via Zoom. Subjects will be guided to mentally simulate the planning and implementation of everyday tasks (e.g., going grocery shopping). The training sessions will last about 15-20 min. We will also record the mental imagery scripts for self-practice on no-training days in the first 4 weeks and for daily homework practice in the subsequent 2-week block. After practice, subjects will be asked to submit a detailed daily mental imagery diary via the Yale REDCap online survey platform. We will structure this diary based on the key elements of mental imagery including the setting of the activity, components of the activity, contextual cues, episodic details, emotional experiences, and vividness and difficulty level of the mental imagery exercise. Subjects will also be called once a week in the last 2 weeks for check-in.

Psychoeducation: Subjects in the PD-Con group will receive psychoeducation 3 times a week for 4 weeks regarding cognitive functioning and brain health in PD. Subjects will receive private video links with pre-recorded PowerPoint lectures covering topics such as basic brain anatomy, neuroplasticity, attention-executive function, memory, speech-communication, hallucinations and delusions, sleep, diet, physical activity, mood disorders, stress, and social bonds. The lectures will last about 15-20 min and will be accompanied by three multiple-choice questions to be completed via REDCap online survey platform to assess content comprehension. On no-lecture days in the first 4 weeks and in the subsequent 2-week block, subjects will receive quizzes covering the lecture topics to be completed via REDCap online survey platform. Subjects will also be called once a week in the last 2 weeks for check-in.

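### A side-effects record is completed after every phone or Zoom contact, and training schedules 14 such contacts in PD-MI against 2 in PD-Con, so the by-group adverse event summary is open to detection bias.

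*Combined protocol and SAP*

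**What the plan says.** Section 5.1.2 defines an adverse event as any untoward physical or psychological occurrence, related to the research or not. It then commits to a by-group summary: "We will submit information summarizing the number and frequency of adverse events experienced by participants in each group". It also promises to say, at reporting, over what period events were collected and whether collection was systematic.

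The routine record tied to remote contacts is described in section 2.3.1, under Confidentiality. It is an online source document whose listed contents end with "details of intervention, and side effects". Its timing is explicit: "After each telephone encounter and Zoom visit this online document will be filled out and maintained with subjects' research records".

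The two arms differ in how often that record is triggered. Under Training period in section 5.1:

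- PD-MI: "Subjects in the PD-MI group will receive personalized training during one-on-one sessions 3 times a week for the first 4 weeks". The mode is live: "Training will be offered via Zoom".
- PD-Con: "Subjects will receive private video links with pre-recorded PowerPoint lectures". Its questions and quizzes are completed in REDCap.
- Both arms: "Subjects will also be called once a week in the last 2 weeks for check-in".

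Sections 4.1.1 and 5.3.2 confirm the contrast in delivery.

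**The concern.** A subject who speaks to staff three times a week has many more occasions to mention a fall, a bad night or low mood than one who watches a recording. Because the definition covers events of any cause, such incidental complaints count. The group comparison then reflects how often each arm is in contact with staff as well as how often events occur.

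Two errors are possible. Imagery training could look less safe than it is, or events in PD-Con could go unseen. The by-group summary is the only comparative safety output the plan describes, and there is no DSMB. The problem cannot be repaired at analysis, because events that were never elicited cannot be recovered.

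**Working it through.** The documents give no total of contacts and no adverse event rate, so there is no plan figure to reproduce. The contacts can be counted.

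**Scheduled remote contacts between Visit 2 and Visit 3, per subject** (section 5.1, Training period)

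| | PD-MI | PD-Con |
|---|---|---|
| Weeks 1-4, live Zoom | 3 × 4 = 12 | 0 |
| Weeks 5-6, check-in calls | 1 × 2 = 2 | 1 × 2 = 2 |
| Total | 14 | 2 |
| Weeks with any contact | 6 of 6 | 2 of 6 |

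With 60 per group (section 4.3.1) and no dropout, this is 60 × 14 = 840 source documents against 60 × 2 = 120. Visit reminders made by phone (section 5.3.2) could add contacts in both arms; their number is not given and they are not counted here.

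**Is there anything that levels this?** Section 5.1.2 says events are monitored in each subject, but gives no question and no schedule. The presence of the team described in section 2.3.1 applies to the in-person experiments, not to training at home. The visit descriptions in section 5.3.3 mention no adverse event enquiry. Section 5.3.2 matches staff time only at research visits.

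**Effect on the recorded ratio, simple model.** Assume equal true rates spread evenly over time, an event always recorded if its week contains a contact, and otherwise recorded with probability r through later recall at a call or visit.

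- Six training weeks: ratio = 6 / (2 + 4r).
- All 18 weeks: the 12 follow-up weeks have no scheduled remote contact in either arm and end at the same Visit 4, so ratio = (6 + 12r) / (2 + 4r + 12r).

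| Later recall r | 6 weeks | 18 weeks |
|---|---|---|
| 0 | 6/2 = 3.0 | 6/2 = 3.0 |
| 0.5 | 6/4 = 1.5 | 12/10 = 1.2 |
| 1 | 6/6 = 1.0 | 18/18 = 1.0 |

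**Second model, as a check.** Each event is recorded at the next contact or visit with probability exp(−lag/τ). Zoom sessions are placed on days 1, 3 and 5 of each of the first 4 weeks, calls on days 35 and 41.5, and Visits 3 and 4 on days 42 and 126. All these placements and the τ values are assumptions.

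| τ (days) | Ratio, 6 weeks | Ratio, 18 weeks |
|---|---|---|
| 7 | 2.74 | 2.09 |
| 14 | 1.96 | 1.55 |
| 28 | 1.48 | 1.24 |
| 56 | 1.24 | 1.10 |
| complete recall | 1.00 | 1.00 |

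With Poisson counts, 60 per group and equal true rates of 0.1 to 1.0 events per subject per 6 weeks (assumed), the chance that PD-MI shows strictly more recorded events in training is 0.84 to above 0.99 at τ = 7, 0.67 to 0.97 at τ = 28, and 0.57 to 0.85 at τ = 56. With complete recall it is 0.44 to 0.48, below one half because ties do not count.

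**The case against.** The strongest reply is that the source document is an institutional form introduced because of Covid-19. Nothing says that it feeds the by-group table, or that staff must put a side-effects question at each session. The case report form is a listed attachment that is not reproduced, so it may contain an adverse event item. Subjects may contact the team at any time, and onset and end are recorded for each event, which allows events to be captured later. Section 5.1.2 promises to disclose the collection approach, and section 5.4 plans no test of adverse events between groups. The study is described as minimal risk, and the physical risks it lists come from MRI, at visits where both arms are observed.

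Much of this limits the size of the problem without removing it. Contact at the subject's own initiative is not equal enquiry. Saying how events were collected does not make collection equal. A low-risk setting means small counts, which a few extra minor complaints can distort.

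Several stronger readings are tempting and are not supported:

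- *The table is certain to show more events in PD-MI.* Full recall gives a ratio of 1.0, and with few events chance can reverse the order.
- *The excess will approach 7:1.* That is the ratio of contacts. The ratio of recorded events depends on recall and is at most 3.0 in the models above.
- *The PD-MI diary is a second adverse event channel.* The emotional experiences it covers are part of the imagery content, and section 5.1.1 describes these surveys in that way.
- *The adverse event table is a stated input to phase 2.* Section 2.3.2 speaks only of knowledge gained from the study in general.
- *The source document is the only adverse event record during training.* It is the only one described with a contact-by-contact schedule; the unseen case report form prevents a firmer statement.

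**Conclusion.** The concern holds as a matter of unequal ascertainment. Followed as written, the plan gives PD-MI 14 scheduled occasions for a side-effects record during training and PD-Con 2, with 12 against 0 in the first 4 weeks, and describes no common enquiry to offset this. The by-group summary is therefore open to detection bias and is expected to record more events in PD-MI under equal true rates.

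The direction rests on one assumption: that some events not raised near the time are never reported later. The size rests on recall values that the documents do not give. The plausible range runs from no distortion to a threefold excess, and at half recall the excess is smaller over 18 weeks than over training alone. This is a worthwhile and inexpensive improvement to the safety reporting; it does not touch the efficacy analyses.

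**What to change.** In sections 5.1.2 and 5.3.3:

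1. Put one identical short adverse event question to both arms through REDCap once a week for the 6 training weeks. Send it as a standalone item, not conditional on completing homework. Section 4.3.2 tolerates homework completion as low as 50%, so an attached item would tie capture to adherence, which may differ by arm.
2. Ask the same question, from a script, at Visits 3 and 4.
3. State that this collection is systematic and is the source of the by-group table.
4. Report events that surface only in Zoom sessions or by spontaneous contact separately, flagged as non-systematic.

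The cost is up to 120 × 6 = 720 short weekly responses over the whole trial, plus one scripted question at each of two visits. Existing staff would need to review the responses promptly enough to meet the 5-day IRB reporting time in section 5.1.2. More minor events will be recorded overall. No extra visits are needed.

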5.2 Study Schedule

See also Figure 4 for study schedule.

Verbal consent will be obtained for the initial screening visit over the phone or via email when the potentially eligible subject is first contacted. Electronically signed informed consent will be obtained at the beginning of the initial Zoom video screening visit via REDCap.

Time estimate for initial screening: 1 hour

There will be a total of 4 in-person visits:

Visit 1: Baseline Clinical Evaluation. Subjects will undergo detailed clinical evaluations to determine disease severity and level of cognitive functioning.

Time Estimate: 3 hours

Visit 2: Baseline Neuroimaging Experiments. Subjects will rate their mental imagery vividness at baseline and perform fMRI tasks in the scanner. Subjects will also receive instructions on their respective training and homework assignments.

Time Estimate: 2 hours

Training: Subjects will receive their respective training 3 times per week for 4 weeks. On non-training days during the week and in the subsequent 2-week block, subjects will complete homework.

Visit 3: 6-Week Post-Intervention Assessments. All subjects will return for repeat cognitive evaluations as in Visit 1, and mental imagery vividness rating and fMRI scans as in Visit 2.

Time Estimate: 3 hours

Visit 4: 12-Week Post-Completion Assessments. All subjects will return for repeat cognitive evaluations and fMRI tasks. The same procedures as described in Visit 3 will be followed.

Time Estimate: 3 hours

5.3 Informed Consent

Consent forms describing in detail the study intervention, study procedures, and risks will be given to the participants and written documentation of informed consent will be required prior to starting intervention/administering study intervention. Consent form will be emailed to the

research participant. The authorized study member will obtain consent electronically at the start of the initial screening visit via Zoom.

The written consent form is submitted with this protocol.

5.3.1 Screening

The research assistant, [name], will screen subjects over the phone for MRI safety and medical history. Eligible subjects will then be scheduled for a Zoom online video platform call to electronically sign the consent form via REDCap and undergo video-screening for demographic data, global cognition, and functional abilities. The initial screening will last approximately 1 hour.

5.3.2 Recruitment, Enrollment and Retention

Recruitment

We will recruit individuals with PD directly through the Yale Movement Disorders outpatient clinics. The outpatient clinics in the new Yale PD Comprehensive Care Center will also be a source of recruitment. Potentially eligible PD patients will be informed about the study during their visit at the clinics and provided with the study flyer. Interested patients will be contacted directly by the study team for initial screening. More specifically, [name] and [name] are both movement disorders neurologists who have a direct or indirect treatment relationship with PD patients in the Yale Movement Disorders Clinics. They (or the research assistant [name]) will inform the patients with whom they have a direct treatment relationship either during clinic visits or via phone. [name] and [name] will review the EPIC clinic visit progress notes of PD patients with whom they are not in a direct treatment relationship to determine eligibility (based on DOB, sex, past medical history, and movement exam scores). They will then ask the treating movement disorders neurologists in their practice to inform these potentially eligible PD patients about the study and ask them for permission to release contact information.

We will also attend meetings at the local PD support groups and nonprofit organizations (e.g., American PD Association Connecticut Chapter, Beat PD Today exercise program) that provide educational and wellness programs for the greater PD community in Connecticut to present the proposed study to potential subjects.

Recruitment flyers (see attached) will also be mailed to the providers at the neurology practices in Connecticut who care for patients with PD. Letters including study flyers will also be mailed to interested candidates who have agreed to be contacted by the study investigators.

In addition, the recruitment services at the YCCI including the YCCI clinical trials website and the YCCI social media support will be used to advertise the study. The same language in the study flyer will be used for advertisements. We will also utilize the YCCI recruitment database. YCCI has an ever growing “Help us Discover” database of more than 14,000 individuals who have expressed interest in clinical research at Yale. Emails are sent periodically to the group to maintain engagement and research interest. Researchers and study teams have found the communications have increased interest and clinical trial recruitment after each YCCI email campaign.

Lastly, we will also make use of the recruitment services offered by JDAT (EPIC/MyChart alerts & mailing) and Department/Center newsletters.

Enrollment

See Table 2. Planned Enrollment and explanations in Section 4.3.

Retention

We will ensure that the logistics of the study is straightforward in order to maximize subject compliance and retention. The Yale MRRC and YCCI are located in the Yale School of Medicine campus in close proximity to each other. No other research sites will be involved. We will email subjects the video link of a virtual tour of the MRRC and YCCI outpatient facility, so that they can familiarize themselves with the research sites (lobby, waiting area, behavioral testing rooms, scanner rooms, etc.) prior to their visit. Subjects will also be provided written directions and maps to the research site. Parking is always available in two garages near both research sites. Subjects who do not feel comfortable driving and have nobody else to drive them will be offered transportation. Subjects will be compensated for their participation and for travel expenses (e.g., parking, cab ride).

The one-on-one mental imagery training for the experimental group and psychoeducation for the control group will be administered via the Zoom video platform and private video links, respectively, eliminating the burden of in-person visits on the subjects. The video visits will be scheduled at convenient times for the subjects. Several surveys will also be administered online via the Yale REDCap survey platform, which will provide the subjects with enough time and flexibility to fill them out. All subjects will also submit their homework via REDCap, which will allow us to monitor compliance in a timely fashion.

At the first screening visit, the study procedures, expectations, and the importance of their participation will be explained to subjects in detail and all questions will be answered. Plans to minimize risk and discomfort and to ensure safety and confidentiality will be discussed, and subjects will be encouraged to ask questions. At their first visit, subjects will receive a study folder containing brief descriptions of the study procedures, specific instructions for each research visit, calendar of research activities throughout the study period, and appointment cards. The subsequent visits will be scheduled considering the best availability of the subjects to avoid scheduling conflicts. Regular reminders for upcoming visits will be sent via email and/or phone. Subjects will be encouraged to contact the study team via email or phone anytime if they had questions, concerns, or requests.

In our previous imagery study, the dropout rate was approximately 15%. This included subjects who did not complete the study and those who were not compliant with homework requirements. The dropout rate was not significantly different between the experimental and control groups. All others (a total of 44) successfully completed four research visits spanning 6-8 weeks each of which lasting 2-3 hours. Subjects remained fully compliant and motivated throughout the study period. We expect a similar level of compliance and motivation, and not more than 15% dropout in the current study. We also considered specific factors regarding the control group in the current proposal that will help minimize the attrition rate. The control group will be actively engaged in psychoeducation tasks during video lectures and will complete homework (quizzes). Time spent with staff during research visits will also be matched between the experimental and control groups. We will explain to all subjects that their effort and compliance will play a major role in their success and potential benefit from the intervention. Therefore, we do not anticipate attrition problems related to subject motivation.

In our sample size calculations, we have accounted for a 15% dropout rate between visits. If we experience a higher rate, we will identify the challenges of study participation and determine new or additional ways to facilitate retention (e.g., adjust the start time of visits, offer meals during long visits).

In summary, we believe that the study design and logistics, as well as the resources for clinical research available at Yale will allow us to reach the recruitment and retention goals of the study within the proposed time frame.

